## Definition of SAE

An SAE is defined as any untoward medical occurrence that, at any dose:

a) Results in death

b) Is life-threatening  The term ‘life-threatening’ in the definition of “serious” refers to an event in which the subject was at risk of death at the time of the event. It does not refer to an event, which hypothetically might have caused death, if it were more severe.

c) Requires inpatient hospitalization or prolongation of existing hospitalization  In general, hospitalization signifies that the subject has been detained (usually involving at least an overnight stay) at the hospital or emergency ward for observation and/or treatment that would not have been appropriate in the physician’s office or outpatient setting. Complications that occur during hospitalization are AEs. If a complication prolongs hospitalization or fulfils any other serious criteria, the event is serious. When in doubt as to whether “hospitalization” occurred or was necessary, the AE should be considered serious.  Hospitalization for elective treatment of a pre-existing condition that did not worsen from baseline is not considered an AE.

d) Results in persistent disability/incapacity
 
 
• The term disability means a substantial disruption of a person’s ability to conduct normal life functions.
 
• This definition is not intended to include experiences of relatively minor medical significance such as uncomplicated headache, nausea, vomiting, diarrhea, influenza, and accidental trauma (eg, sprained ankle) which may interfere with or prevent everyday life functions but do not constitute a substantial disruption.
 

e) Is a congenital anomaly/birth defect


f) Other situations:
 
 
• Medical or scientific judgment should be exercised in deciding whether SAE reporting is appropriate in other situations such as important medical events that may not be immediately life-threatening or result in death or hospitalization but may jeopardize the subject or may require medical or surgical intervention to prevent 1 of the other outcomes listed in the above definition. These events should usually be considered serious.  Examples of such events include invasive or malignant cancers, intensive treatment in an emergency room or at home for allergic bronchospasm, blood dyscrasias, or convulsions that do not result in hospitalization, or development of drug dependency or drug abuse.
 

## Recording and Follow-up of AE and/or SAE

AE and SAE Recording

 
• When an AE/SAE occurs, it is the responsibility of the Investigator to review all documentation (eg, hospital progress notes, laboratory reports, and diagnostics reports) related to the event.
 
• The Investigator will then record all relevant AE/SAE information in the CRF. Each event must be recorded separately.
 
• It is not acceptable for the Investigator to send photocopies of the subject’s medical records to ██████ Safety in lieu of completion of the /AE/SAE CRF page.
 
• There may be instances when copies of medical records for certain cases are requested by ██████ Safety. In this case, all subject identifiers, with the exception of the subject number, will be redacted on the copies of the medical records before submission to ██████ Safety.
 
• The Investigator will attempt to establish a diagnosis of the event based on signs, symptoms, and/or other clinical information. Whenever possible, the diagnosis (not the individual signs/symptoms) will be documented as the AE/SAE.
 

Assessment of Intensity

The Investigator will make an assessment of intensity for each AE and SAE reported during the study and assign it to 1 of the following categories:
 
 
• Mild: An event that is easily tolerated by the subject, causing minimal discomfort and not interfering with everyday activities.
 
• Moderate: An event that causes sufficient discomfort and interferes with normal everyday activities.
 
• Severe: An event that prevents normal everyday activities. An AE that is assessed as severe should not be confused with a SAE. Severe is a category utilized for rating the intensity of an event; and both AEs and SAEs can be assessed as severe.
 
 
An event is defined as ‘serious’ when it meets at least 1 of the predefined outcomes as described in the definition of an SAE, NOT when it is rated as severe.

Assessment of Causality

 
• The Investigator is obligated to assess the relationship between study treatment and each occurrence of each AE/SAE. The AE must be characterized as unrelated, possibly related, and related. 
 
○ “Unrelated” clinical event with an incompatible time relationship to study drug administration, and that could be explained by an underlying condition or other drugs or chemicals or is incontrovertibly not related to the IP
 
○ “Possibly related” Clinical event with a reasonable time relationship to study drug administration, and that is unlikely to be attributed to concurrent condition or other drugs or chemicals
 
○ “Related” Clinical event with plausible time relationship to study drug administration and that cannot be explained by concurrent condition or other drugs or chemicals
 
 
 
• The Investigator will use clinical judgment to determine the relationship.
 
• Alternative causes, such as underlying disease(s), concomitant therapy, and other risk factors, as well as the temporal relationship of the event to study treatment administration will be considered and investigated.
 
• The Investigator will also consult the IB and/or Product Information, for marketed products, in his/her assessment.
 
• For each AE/SAE, the Investigator must document in the medical notes that he/she has reviewed the AE/SAE and has provided an assessment of causality.
 

- There may be situations in which an SAE has occurred and the Investigator has minimal information to include in the initial report to ██████████ Safety. However, it is very important that the Investigator always make an assessment of causality for every event before the initial transmission of the SAE data to ██████████ Safety.
- The Investigator may change his/her opinion of causality in light of follow-up information and send a SAE follow-up report with the updated causality assessment.
- The causality assessment is one of the criteria used when determining regulatory reporting requirements.

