#### **4.5 Study Stopping Criteria**

##### **4.5.1 Stopping Criteria for Individual Subjects**

Dosing for any individual subject will be stopped if the subject experiences a SAE or a clinically significant possibly drug related AE, which in the opinion of the study physician, Investigator, or Sponsor's medical representative, warrants discontinuation of the study for that subject's wellbeing. Details on subject withdrawal are presented in Section 7.0.

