### **8.3.8 Disease-related Events and/or Disease-related Outcomes Not Qualifying as AEs or SAEs**

The following disease-related events (DREs) are common in subjects with GPP and can be serious/life-threatening:

- Flare of GPP.

Because these events are typically associated with the disease under study, they will not be reported according to the standard process for expedited reporting of SAEs even though the event may meet the definition of a SAE. These events will be recorded on the corresponding eCRF page in the subject's eCRF.

***NOTE:** If either of the following conditions applies, then the event must be recorded and reported as an SAE (instead of a DRE):*

*The event is, in the Investigator's opinion, of greater intensity, frequency, or duration than expected for the individual subject.*

**OR**

*The Investigator considers that there is a reasonable possibility that the event was related to study treatment.*

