19. SAFETY OUTCOMES

All safety data (AEs, SAEs, vital signs, ECGs, and clinical laboratory assessments at each specific time point) will be listed and summarized descriptively using the SAF. All AEs will be coded using the latest version of the Medical Dictionary for Regulatory Authorities (MedDRA). For the handling of partial dates for AEs, see Appendix 2 of this document.

All AEs will be classified by Intensity, Seriousness and Causality.

Intensity will be assessed as Mild, Moderate or Severe. If the Intensity of an AE changes, it's overall Intensity will be classified by the worst case of the multiple occurrences.

- Mild events are usually transient and do not interfere with the subject's daily activities.
- Moderate events introduce a low level of inconvenience or concern to the subject and may interfere with daily activities.
- Severe events interrupt the subject's usual daily activity.
- Missing severity will be assumed to be the worst severity case i.e. 'severe'; however, in the listing, it will be displayed as missing.

Seriousness will be assessed as either Not Serious or Serious, which is defined as:

- Resulting in death
- Life-threatening
- Requiring inpatient hospitalization or prolonging of existing hospitalization
- Resulting in persistent disability/incapacity
- Congenital anomaly/birth defect

The causal relationship between the study drug and the AE will be characterized as "Unrelated", "Possibly Related", or "Related". Missing relationship will be assumed to be the worst severity case (Related) in data summary tables; however, in listings it will be displayed as missing. If a subject reports the same AE more than once within an SOC/PT, the AE with the worst -case Intensity and Relationship to the study treatment will be used in the corresponding summaries. An AE that occurred one or more times on treatment period will contribute only one observation to the numerator. The denominator comprises all safety subjects exposed to ANB019.

Only TEAEs will be summarized and presented by SOC and PT. Listings will include all AEs, with TEAEs flagged.

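### The three causality definitions in Appendix 4 are neither exhaustive nor mutually exclusive, so ambiguous adverse events have no defined class

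*Protocol*

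**What the plan says.** Protocol Appendix 4 (Assessment of Causality) sets a forced choice: "The AE must be characterized as unrelated, possibly related, and related". The definitions are:

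- *Unrelated* is given as a "clinical event with an incompatible time relationship to study drug administration, and that could be explained by an underlying condition or other drugs or chemicals". A second route is an event that is beyond dispute not due to the product.
- *Possibly related* is given as "Clinical event with a reasonable time relationship to study drug administration, and that is unlikely to be attributed to concurrent condition or other drugs" (the sentence goes on to include chemicals).
- *Related* is given as "Clinical event with plausible time relationship to study drug administration and that cannot be explained by concurrent condition or other drugs or chemicals".

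The same appendix tells the Investigator to apply clinical judgment and to look into alternative causes and timing. It adds that causality is one of the inputs to regulatory reporting.

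Other sections use relatedness in different words. Section 4.5.1 refers to a "clinically significant possibly drug related AE". Section 8.3.8 turns a GPP flare into a reportable SAE if "The Investigator considers that there is a reasonable possibility that the event was related to study treatment" (or if the flare is worse than expected for that subject). Section 6.7 ties reporting and follow-up of significant AEs to the Investigator's view that they are drug-related. Protocol Section 9.4.5.1 and SAP Section 19.1.1 tabulate TEAEs by relationship.

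SAP Section 19 repeats the three labels ("The causal relationship between the study drug and the AE will be characterized as" one of them) without definitions. It counts a missing relationship as *Related* in the tables.

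**The concern.** A causality scale should give each event exactly one class, and the middle class should hold the uncertain events. Here the middle class is defined by another cause being unlikely, which is closer to what most readers would call probable. An event that is possibly, but not probably, due to ANB019 does not meet the definition that carries that name.

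The trial's setting makes such events plausible. The protocol describes fever, leukocytosis and raised CRP as features of GPP. It allows study drug to start before the taper of a systemic therapy has ended, so other drugs are a live explanation too. Safety is a primary objective and there is no comparator arm. With about 10 subjects at 8 to 10 centers, one or two events coded differently would visibly change a table by relationship.

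**Working it through.** The plan gives no figure on this point, so the check is a logical enumeration of the Appendix 4 definitions.

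**Inputs.** Timing has two levels, incompatible or reasonable; the words *reasonable* and *plausible* are treated as the same level. The alternative cause has three levels: cannot explain the event, could but is unlikely to, or could well explain it. That gives 2 × 3 = 6 combinations. Events beyond dispute not due to the product are set aside, because they are *Unrelated* by the second route.

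**Rules applied.**
- *Unrelated*: incompatible timing AND another cause could explain the event, even if it is unlikely to.
- *Possibly related*: reasonable timing AND another cause is unlikely. A cause that cannot explain the event is, a fortiori, unlikely.
- *Related*: reasonable timing AND no other cause can explain the event.

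| Timing | Another cause | Class as written |
|---|---|---|
| Incompatible | Cannot explain | None |
| Incompatible | Unlikely | Unrelated |
| Incompatible | Could well explain | Unrelated |
| Reasonable | Cannot explain | Possibly related and Related |
| Reasonable | Unlikely | Possibly related |
| Reasonable | Could well explain | None |

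**Result.** Of 6 combinations, 2 have no class, 1 has two classes and 3 have exactly one (2 + 1 + 3 = 6). If the explanation required for *Unrelated* had to be a credible one, the second row would also be empty and 3 of 6 would have no class. The last row, which is the main gap, does not depend on that reading.

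**Does other text fill the gap?** The judgment and alternative-cause clauses say what to weigh, not which class follows. SAP Section 19 adds no definitions. Its missing-to-*Related* rule works only if the field is blank, and Appendix 4 requires an assessment for each event.

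**The same six combinations under the wording proposed below.** All three incompatible-timing rows become *Unrelated*. Reasonable timing with no other possible cause becomes *Related* only. Reasonable timing with an unlikely alternative becomes *Possibly related*. Reasonable timing with a credible alternative becomes *Possibly related*, unless there is clear evidence of the other cause, in which case it is *Unrelated*. Both gaps and the overlap close.

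**The case against.** The strongest reply is that little turns on this label.

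- Section 8.3.1 requires SAEs to be reported within 24 hours up to the EOS visit whatever their causality, and Section 8.3.6 requires expedited AESI reporting with no causality condition.
- GPP flares follow Section 8.3.8. Laboratory findings and signs associated with the disease are not AEs unless more severe than expected.
- Section 4.5.1 covers any SAE and turns on medical opinion. It does not cite Appendix 4.
- TEAEs are summarized by system organ class and preferred term regardless of relationship, and every AE is listed, which in about 10 subjects leaves each one visible.

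All of this stands, and it limits the consequences. It does not supply the missing class.

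A reader might go further in three ways that the documents do not support.

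- *That these are the commonest events.* The documents give no frequency for them.
- *That causality is biased toward Unrelated.* A literal reader is barred from that label too, because the timing is compatible. Left to judgment, a site could as well choose *Possibly related* by its ordinary meaning.
- *That investigator causality is the main filter for a drug signal.* The tables and listings that ignore relationship contradict this.

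Nor is Section 8.3.8 a second error of equal weight. It governs only how flares are reported, although its standard is not tied to Appendix 4.

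**Conclusion.** The definitional fault holds on the face of the text. Two kinds of event have no class: reasonable timing with a credible alternative cause, and incompatible timing with no alternative explanation (where the event is not beyond dispute unrelated). One kind, reasonable timing with no other explanation, has two. The result is undefined coding that may vary between sites. There is a risk of bias but no demonstrated direction, and its size cannot be estimated from the documents.

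The effect falls mainly on non-serious AEs, the TEAE tables by relationship, the causality input to regulatory reporting, and the follow-up that Section 6.7 ties to relatedness. In-study SAE reporting (outside the flare pathway), AESI reporting and the overall TEAE tables are unaffected. The conclusion assumes that sites read the definitions as written and that no completion guideline outside these documents supplies a rule. This is a should-fix clarification, not a threat to the trial's main outputs.

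**What to change.** In Appendix 4:

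- *Possibly related*: a reasonable time relationship where a causal role of ANB019 cannot be excluded, even if concurrent disease or other drugs could also explain the event, and which does not meet *Related*.
- *Unrelated*: an incompatible time relationship, or clear evidence of another cause. State that this is the complement of a causal role that cannot be excluded, so that no new gap opens.
- *Related*: unchanged.

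Reconcile the relatedness wording in Sections 4.5.1 and 8.3.8 with these definitions, leaving the clinical rules themselves as they are. SAP Section 19 needs only a cross-reference to the revised definitions. Have sites re-check the causality of AEs already coded, with changes kept in the audit trail.

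The cost is appendix wording, a line in the eCRF completion guidance and a re-check in about 10 subjects. The downside is that somewhat more events may be labelled drug-related.

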#### Follow-up of AEs and SAEs

- The Investigator is obligated to perform or arrange for the conduct of supplemental measurements and/or evaluations as medically indicated or as requested by ██████████ Safety to elucidate the nature and/or causality of the AE or SAE as fully as possible. This may include additional laboratory tests or investigations, histopathological examinations, or consultation with other health care professionals.
- If a subject dies during participation in the study, the Investigator will provide ██████████ Safety with a copy of any postmortem findings.
- New or updated information will be recorded in the originally completed CRF.
- The Investigator will submit any updated SAE data to the ██████████ Safety within 24 hours of receipt of the information.

### Reporting of SAEs

#### SAE Reporting to ██████████ Safety via an Electronic Data Collection Tool

- The primary mechanism for reporting an SAE to ██████████ Safety team will be the electronic data collection tool.
- If the electronic system is unavailable for more than 24 hours, then the study center will use the paper SAE data collection tool (see next section).
- The study center will enter the SAE data into the electronic system as soon as it becomes available.
- After the study is completed at a given study center, the electronic data collection tool will be taken off-line to prevent the entry of new data or changes to existing data.
- If a study center receives a report of a new SAE from a subject or receives updated data on a previously reported SAE after the electronic data collection tool has been taken off-line, then the study center can report this information on a paper SAE form (see next section) or (see next section) and send the paper SAE form to ██████████ Safety team via facsimile transmission.
- Contacts for SAE reporting can be found in SAE form.

#### SAE Reporting to ██████████ Safety via Paper CRF

- Facsimile transmission of the SAE paper CRF is the preferred method to transmit this information to the ██████████ Safety team.
- In rare circumstances and in the absence of facsimile equipment, notification by telephone is acceptable with a copy of the SAE data collection tool sent by overnight mail or courier service.
- Initial notification via telephone does not replace the need for the Investigator to complete and sign the SAE CRF pages within the designated reporting time frames.
- Contacts for SAE reporting can be found in SAE reporting form.

## Appendix 5 Excluded Medications/Therapy

Excluded medications/therapy is listed below. The use of an excluded medication/therapy is a protocol violation and must be recorded in the eCRF.

Any therapy likely to have efficacy in GPP or psoriasis is prohibited. If treatment with any of these prohibited treatments is essential then the subject must notify the study team and they will be withdrawn from the trial.

All treatments likely to have efficacy in GPP need to be discontinued prior to treatment initiation (prior to Day 1) with washout periods as stipulated in Table 6.

A tapering washout of systemic therapies (eg, cyclosporine, methotrexate, and retinoids) can be used and the study drug can be introduced before the end of the washout period. Systemic conventional medications (eg, cyclosporine, methotrexate, and retinoids) must be stopped at the day the study drug has been administered.

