### **6.5.1 Rescue Medicine**

Rescue medication will be directed by the Investigator as needed. Rescue medication in the form of topical corticosteroids (eg, betamethasone valerate ointment and cream, mometasone furoate ointment and cream) can be used during the study for a period of up to 1 week on a daily basis on affected areas to provide symptomatic relief. The introduction of any rescue medication must be communicated and discussed with the Medical Monitor. Rescue medication will be provided by the site and reimbursed by the Sponsor.

The use of rescue medications should be delayed, if possible, for at least 1 month following the administration of study treatment. Rescue medication may be used at the Investigator's discretion only if medically indicated for the wellbeing of the subject. The date and time of rescue medication administration as well as the name and dosage regimen of the rescue medication must be recorded.

The addition of any systemic psoriasis medication that is likely to impact psoriasis signs and symptoms (eg, cyclosporine, methotrexate, and retinoid) will require the subject to be withdrawn from the study.

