### **7.2 Subject Discontinuation/Withdrawal from the Study**

A subject may withdraw from the study at any time at his/her own request, or may be withdrawn at any time at the discretion of the Investigator for safety, behavioral, compliance, or administrative reasons.

In case of early withdrawal from the study drug and study, the subject will be required to attend the ET visit (see the Schedule of Activities in Section 1.3). Subjects must be withdrawn from the study under the following circumstances, any significant AE which in the opinion of the Investigator is related to the study drug or SAE, or pregnancy occurring through the EOS visit and should be followed-up until outcome:

- Prior to study treatment administration, the Investigator decides that the subject should be withdrawn or is at risk. If this decision is made because of an AE or a clinically significant laboratory value, the study drug should not be administered and appropriate measures are to be taken. AnaptysBio Inc. and/or ██████ is to be notified immediately.
- Significant deviation/lack of compliance with protocol other than the use of excluded/prohibited medications.
- Use of any excluded/prohibited medications that in the opinion of the Investigator necessitates the subject being withdrawn ([Appendix 5](#)).
- Termination of the study by the Investigator or Sponsor.
- Pregnancy ([Appendix 6](#) and Section 8.3.5 Pregnancy).

- New information suggests taking part in the study may not be in the participant's best interest.

If the subject withdraws consent for disclosure of future information, the Sponsor may retain and continue to use any data collected before such a withdrawal of consent.

If a subject withdraws from the study, he/she may request destruction of any samples taken and not tested, and the Investigator must document this in the study center study records.

See Schedule of Activities (Section 1.3) for data to be collected at the time of study discontinuation and follow-up and for any further evaluations that need to be completed.

Subjects withdrawing from the study prematurely for reasons other than a study drug related AE may be replaced at the discretion of the Investigator and Sponsor to ensure the required number of evaluable subjects.

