**Table 6 List of Excluded Medications**

Treatment	Washout period
Topical medication (including corticosteroid, retinoids or vitamin A or D analog preparations, tacrolimus, calcineurin inhibitor, topical H1 and H2 antihistamines, tar preparations, keratolytics, topical antimicrobials, other medicated topical agents) or herbal preparation	2 weeks
Methotrexate, cyclosporin, acitretin, alitretinoin, Fumaric acid esters, and corticosteroids or any other immunosuppressant or immunomodulating drugs	4 weeks
Anti-tumor necrosis factor/interleukin (IL-12/IL-23) and IL-17 or any other mAbs	3 months or 5 half -lives
Cyclophosphamide	6 months
Phototherapy or PUVA	4 weeks
Antibiotics and antivirals	Topical: 2 weeks Systemic: 4 weeks
Other investigational drugs	30 days or 5 half-lives (whichever is longer)
Live attenuated vaccines	3 months

Abbreviations: mAbs = monoclonal antibodies; PUVA = psoralen and ultraviolet A.

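### Protocol Section 6.5.1 permits topical corticosteroid rescue that Appendix 5 excludes, and the SAP has no rule for responder status after rescue

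*Protocol*

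**What the plan says.** Protocol Section 6.5.1 provides for "Rescue medication in the form of topical corticosteroids" and says that these "can be used during the study for a period of up to 1 week on a daily basis on affected areas". Any rescue has to be discussed with the Medical Monitor. The only withdrawal rule in that section concerns systemic treatment: "The addition of any systemic psoriasis medication that is likely to impact psoriasis signs and symptoms". On timing it says: "The use of rescue medications should be delayed, if possible, for at least 1 month following the administration of study treatment".

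Protocol Section 6.5 refers to Appendix 5 for excluded treatments. Appendix 5 states: "Any therapy likely to have efficacy in GPP or psoriasis is prohibited". It classes use of an excluded medication as a protocol violation. If a prohibited treatment is essential, "the subject must notify the study team and they will be withdrawn from the trial". The first row of Table 6 begins "Topical medication (including corticosteroid, retinoids or vitamin A or D analog preparations" and gives a 2-week washout. Neither the appendix nor the table mentions rescue.

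Protocol Section 7.2 lists among its grounds for withdrawal "Use of any excluded/prohibited medications that in the opinion of the Investigator necessitates the subject being withdrawn", so there the decision rests on judgement.

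In the SAP, Section 14 lists and summarizes rescue medication. Section 17.1.2 leaves a missing responder status missing and carries Week 4 non-responders forward as Week 16 non-responders; it does not mention rescue. Section 17.1.3 analyses the FAS with everyone enrolled in the denominator. Section 17.1.4 plans no sensitivity analysis.

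**The concern.** One event, a short course of topical corticosteroid after dosing, is allowed on one page of the protocol and is a violation that can end participation on another. The primary endpoint depends on which page is followed, because the SAP treats a subject who stays and a subject who leaves differently and has no rescue rule that would bring them together.

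If the subject stays, the Week 16 rating is used as observed and may partly reflect the steroid. The documents themselves treat topical corticosteroid as able to influence the assessments, since they require a washout before baseline. Yet Section 6.5.1 sets no interval between rescue and an efficacy visit, whereas even bland emollients are barred in the 24 hours before a visit. The bar for response is also low: in SAP Table C, an unchanged mJDA total with meaningful improvement in one component, such as area of erythema, is a response.

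The study is exploratory and descriptive, but this proportion is its primary efficacy result, and the interim look at it may guide later studies (protocol Section 9.5).

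**Working it through.** The plan gives no figure to reproduce: the sample size is expressly not based on power and no hypothesis is tested. The check is a comparison of the texts, followed by the effect on the Week 16 proportion.

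**Texts side by side, for topical corticosteroid used after dosing**

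| Source | Allowed? | Withdrawal? |
|---|---|---|
| Protocol 6.5.1 | Yes, up to 1 week | Not for topical use; only for added systemic medication |
| Protocol Appendix 5 and Table 6 | No; a protocol violation | Yes, if the treatment is essential |
| Protocol 7.2 | Applies to prohibited medication | If the Investigator judges it necessary |

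Section 6.5.1 allows rescue only when medically indicated. That trigger largely overlaps with treatment being essential in Appendix 5, but the consequence differs.

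**Who can move the Week 16 proportion**

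- A rescued subject who would be a non-responder at Week 16: no change.
- A Week 4 non-responder: already terminated and fixed as non-responder, so no change.
- A subject rescued only after the Week 16 visit (Day 113 ±2): no change.
- A would-be responder rescued before that visit: counts 1 in the numerator if kept and 0 if withdrawn. Withdrawal leaves the status missing, while the denominator is unchanged.

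**Size**

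Inputs: N = 10 (protocol 9.2, approximate); x = Week 16 responders if all rescued subjects are kept (assumed); k = rescued would-be responders withdrawn before Week 16 (assumed). The proportion is (x − k)/N, so the change is −k/N. For k = 1 this is −1/10, or −10 points. With x = 8 and exact Clopper-Pearson 95% intervals:

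| k | Responders | Proportion | 95% CI |
|---|---|---|---|
| 0 | 8/10 | 80% | 44.4 to 97.5% |
| 1 | 7/10 | 70% | 34.8 to 93.3% |
| 2 | 6/10 | 60% | 26.2 to 87.8% |
| 3 | 5/10 | 50% | 18.7 to 81.3% |

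The step for k = 1 is the same at other assumed counts: from 5/10 to 4/10 (50% to 40%) up to 10/10 to 9/10 (100% to 90%).

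**What the size depends on**

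- Denominator. If only observed statuses were counted, 8/10 would become 7/9 = 77.8%, a fall of 80 − 77.8 = 2.2 points. SAP 17.1.3 specifies all enrolled, so the 10-point step applies.
- Replacement. Section 7.2 allows a subject withdrawn for reasons other than a drug-related AE to be replaced. Counting all 11 enrolled gives 8/11 = 72.7% if the replacement responds and 7/11 = 63.6% if not.

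**The case against.** The strongest reply is that Section 6.5.1 is the specific provision and Appendix 5 the general one, so rescue is an implied exception. Exclusion criterion 15 refers to Section 6.5.1 for rescue, and Table 6 has a washout column whose topical entry largely repeats a pre-baseline restriction. This reading is plausible, but neither Appendix 5 nor Table 6 states it. The appendix covers use during the trial, since it provides for withdrawal, and it states an exception where one is meant, as for tapering washout. Even if the reading is accepted, SAP 17.1.2 still has no rescue rule.

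Four stronger readings might be inferred and are not supported:

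- *Every rescue is subject to three competing rules.* Section 7.2 concerns prohibited medication. It governs rescue only if rescue is already classed as prohibited. Its difference from Appendix 5 is real but concerns prohibited drugs in general.
- *Every rescued subject shifts the primary proportion by 10 points.* Only the last group listed in the working does, and only at Week 16. Week 4 is largely shielded by the requested delay, though not fully, because the delay applies only if possible.
- *Per-protocol results are at risk.* The two texts disagree on whether a violation occurred, but SAP 17.1.3 and 17.2.3 run primary and secondary efficacy on the FAS. The only planned use of the per-protocol set found in the SAP is a disposition count.
- *Centres are free to diverge.* Discussion with the Medical Monitor limits this, although it does not settle which text prevails.

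**Conclusion.** Wrong as written. The current text of Section 6.5.1 and of Appendix 5 with Table 6 cannot both be followed literally, Section 7.2 differs from Appendix 5 on withdrawal, and the SAP leaves responder status after rescue undefined.

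The effect is up to about 10 points on the Week 16 proportion for each rescued would-be responder withdrawn before that visit. This rests on N of about 10, the all-enrolled denominator and no replacement. The documents do not say how many subjects are expected to need rescue, so the total effect cannot be stated and may be zero. A one-subject shift is small beside the width of the intervals at this sample size. It is nevertheless avoidable, because it comes from wording and not from sampling.

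**What to change.** Reconcile protocol Sections 6.5.1 and 7.2 and Appendix 5 with Table 6, so that one rule covers topical corticosteroid use after dosing, including whether it is a violation and whether it leads to withdrawal. Which rule is right is a clinical decision that this review does not make.

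Then add to SAP 17.1.2 one pre-specified rule for responder status at Weeks 4 and 16 after topical corticosteroid use. One option is to count use before the visit as non-response in the primary table, whether or not the subject was withdrawn, and to show the as-observed result beside it. In the example with one rescued would-be responder, the primary table then gives 8 − 1 = 7 of 10 whether the subject is kept or withdrawn, so the handling no longer affects the result. Other rules are defensible if fixed in advance. The SAP should also say how replaced subjects enter the denominator.

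The cost is wording in both documents and one extra column. The downside of the example rule is that the reported response rate may be lower, since a response that owes nothing to the steroid would not be counted in the primary table.
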